Stool microscopy (*Giardia*, *Cryptosporidia*, *E. histolytica*), Stool culture (vibrios, shigella, salmonella and campylobacter) and urine analysis will be done.

Randomization:

After examining the eligibility criteria and informed consent signed by one of the parents/legal guardian, the patients will be randomized to either intervention group (dietary treatment algorithm) or control (standard management). Two strata of randomization list will be prepared by using random table. One stratum will be used for randomization of patients 5 months to 18 months and other stratum 19-36 months. The randomization lists will be prepared and serially numbered in sealed envelopes will be supplied containing the name of the treatment group. The envelopes will be opened by one of the investigators only after a patient has been irrevocably assigned to the study.

Case management

Intervention group

Treatment algorithm:

We have chosen to adapt the WHO algorithm designed for hospitalized children. The components of the treatment algorithm are summarized in Fig. 1, (Adapted from ref. 21) During the observation period, the mothers or other caregivers of the children will be educated to prepare the diet (Table I) and will be advised to feed study Diet (A) containing milk and rice-cereal mixture initially for 7 days. House visits will be done on every alternate days for follow up. During follow-up on day-3, if any treatable stool pathogen was identified from specimen obtained on Day 1, antimicrobial therapy will be provided for administration at home. Any skin infection, mild respiratory tract infection or urinary tract infection will also be treated with antimicrobial orally at home. Patients with skin infection will be treated with cloxacillin 50 mg/kg/day in 4 divided doses. Mild respiratory tract infection will be treated with amoxicillin 100 mg/kg/day in 3 divided doses. Urinary tract infection will be treated according to the culture and sensitivity results. All requisite medicines will be provided to all study patients, and ingredients of diets will be supplied to the mothers of the patients of the intervention group only.

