After cooked volume	1000 ml	After cooked volume	1000 ml
Energy	67kcal/100ml	Energy	70 kcal/100 ml
Protein	4.4 gm/100ml	Protein	1.88 g/100 ml
PER*	8%	PER	10%

Table 2. Composition of Multivitamin drop (Composition per 1 ml)

Vitamin A U.S.P.	5000 IU
Vitamin D B.P.	640 IU
Ascorbic Acid (C) B.P.	50 mg
Thiamine Hcl (B ₁)	1.6 mg
Riboflavin Sodium Phosphate (B ₂) B.P.	1.37 mg
Pyridoxine B.P. (B ₆) U.S.P.	1.0 mg
Nicotinamide B.P.	10.0 mg
D-Panthenol U.S.P.	5.0 mg
Folic acid	0.25 mg

Justification of selection of diet A in the beginning

Dietary treatment algorithm is a well recognised treatment schedule for the nutritional management of children suffering from persistent diarrhoea. In ICDDR hospital, this treatment algorithm is also being followed. Justification of using Diet A initially is that this diet is easy to prepare, culturally acceptable, less modified as compared to Diet B. and less expensive (1 L Diet A costs Tk. 18.00 vs. Tk. 26.00 for Diet B).

Study withdrawal

Patients will be considered withdrawn from the study if a) their parents withdraw informed consent, or b) needs hospital care.

Patients will be considered for hospital care for the following reasons:

a) appearance of signs of some dehydration b) signs of severe infections (e.g. fever, cough, respiratory distress, tachycardia, tachypnoea, reluctant to feeding etc. c) signs of electrolyte imbalance (e.g. less responsive to environments or irritability, abdominal distensions etc.). After hospitalisation, the patients will be managed according to the standard hospital practice. Patients will be followed up even after withdrawn from the study. Data obtained from the withdrawn patients will also be included in the analysis upto the time of withdrawal.

Sample size

Sample size was calculated on the basis of two major outcome variables:

- a) success rate of diet therapy
- b) Growth faltering (percentage of patients experiencing weight loss during the study periods).

Based on the study (21) the sample size of this study is determined to be of 137 in each group on anticipated success rate (combining success of Diet A and Diet B) of 80% in the intervention group against an arbitrary standard success rate of 65% in the control group, considering a significance level of 5% and power of 80%. Assuming a dropout of 15%, a total sample of 320 patients was calculated.

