Statistical analysis

Statistical analysis will be done using SPSS/PC software. Percentage of success of treatment for each dietary intervention and overall success rate will be calculated. Relative risk ratios and their associated 95% confidence intervals will be calculated to identify variables (e.g. inappropriately making and feeding the diet, associated other infections, education of mothers, family income, no. of children in the family, source of drinking water, antibiotic use before admission, type of dehydration before intervention, frequency of stool etc.) that were related to the treatment failure. Overall success rate (the number of patients recovered at the end of 10 days) in the intervention group will be compared with that of control group. The number of patients lost weight will also be compared between the groups.

Adjusted analysis will be done by constructing life tables of the two groups and will be compared by log rank test.

Ethical Assurance for Protection of Human Rights

Describe in the space provided the justifications for conducting this research in human subjects. If the study needs observations on sick individuals, provide sufficient reasons for using them. Indicate how subject's rights are protected and if there is any benefit or risk to each subject of the study.

This intervention study will be conducted among the children under 5 years of age because these children are the sufferers from this illness of persistent diarrhoea. Written informed consent will be duly signed by the parents or legal guardians.

There is no risk for this intervention on the other hand they might be benefited from this intervention.

Use of Animals

Describe in the space provided the type and species of animal that will be used in the study. Justify with reasons the use of particular animal species in the experiment and the compliance of the animal ethical guidelines for conducting the proposed procedures.

Not applicable.

Literature Cited

Identify all cited references to published literature in the text by number in parentheses. List all cited references sequentially as they appear in the text. For unpublished references, provide complete information in the text and do not include them in the list of Literature Cited. There is no page limit for this section, however exercise judgment in assessing the "standard" length.

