Personnel: Investigators' salary support has been calculated by per cent of effort. Study Physician will help in taking medical history and physical examination in the hospital and also during home visits. Research Officer will organise the facilities in the hospital, arrange equipment and material needed for examination and training. S/he will also do data entry and will help in data analysis. Research assistant will be engaged in patients' recruitment, educate mothers/caregivers about preparation of feeding of diet, and also supervise the caregivers at home.

Equipment: Weighing scale and other measuring equipments will be purchased for anthropometric measurements. Computer accessories will also be needed.

Laboratory services: Cost of laboratory services has been calculated from the existing rates of laboratory services.

Principal Investigator: Last, first, middle _____

Other Support

Describe sources, amount, duration, and grant number of all other research funding currently granted to PI or under consideration. (DO NOT EXCEED ONE PAGE FOR EACH INVESTIGATOR)

1. WHO 47,000.00 for 1 year
2. Novartis Nutrition 89,000.00 for 2 years

Principal Investigator: Last, first, middle _____

Check List

After completing the protocol, please check that the following selected items have been included.

1. Face Sheet Included

2. Approval of the Division Director on Face Sheet

3. Certification and Signature of PI on Face Sheet, #9 and #10

4. Table on Contents

5. Project Summary

6. Literature Cited

7. Biography of Investigators

8. Ethical Assurance

9. Consent Forms

10. Detailed Budget

Answer to Reviewer # I

1. "Demonstrated ability of caregiver" has been omitted from the protocol. All patients fulfilling other entry criteria will be included. Caregivers of the patient who also do not have economic means for providing the advised diets, the ingredients of the study diet will be supplied during the study period.
2. The envelopes will be opened only after a patient has been irrevocably assigned to the study.
3. The mothers will be taught to prepare Diet B on day 6 when there will be no improvement of diarrhoea with Diet A for 5 days.
4. The patients will be followed up for 4 weeks after diarrhoea resolved.
5. Adjusted analysis will be done by construction of life tables of the patients of the study groups and will be compared by log rank test:
6. Addition of 1 g of salt to Diet A has been omitted.

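### The analysis labelled adjusted is a plain two-group log-rank test that leaves out the age strata used at randomisation; stratify it, or call it unadjusted

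*Protocol*

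**What the plan says.** - **Statistical analysis.** Overall success and the number of children losing weight are to be compared between the groups, with no test named and no mention of age. The section then states: "Adjusted analysis will be done by constructing life tables of the two groups and will be compared by log rank test".
- **Answer to Reviewer # I, item 5.** The same promise is repeated: "Adjusted analysis will be done by construction of life tables of the patients of the study groups and will be compared by log rank test". Neither place names a covariate, stratum or model.
- **Randomization.** "Two strata of randomization list will be prepared by using random table". The first list serves children aged 5 to 18 months, the second those aged 19 to 36 months.
- **Study withdrawal.** Data from withdrawn children count until they leave the study.
- **Sample size.** Planning sets 80% success in the intervention arm, both diets taken together, "against an arbitrary standard success rate of 65% in the control group". The test level is 5%, the power 80%, and an allowance of 15% for dropout leads to 320 children in all.

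Relative risks are planned only to look for factors related to treatment failure. Age is not among the examples listed there.

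**The concern.** To most readers, an adjusted comparison is one in which the treatment effect is estimated or tested allowing for baseline factors. Two life tables compared by an ordinary log-rank test do not do that. A report following the protocol literally would present an unadjusted result under an adjusted label.

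The design and the analysis also part company. The protocol separates children by age at randomisation but does not carry that separation into the one time-to-event test it specifies. If age affects how fast diarrhoea stops, pooling the age groups in the log-rank test can reduce its sensitivity. If the arms are also balanced within age groups, the pooled test becomes conservative.

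**Working it through.** **1. Reproduce the protocol's figure.** For 80% against 65%, two-sided 5%, 80% power and pooled variance under the null:

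n = [1.96 × √(2 × 0.725 × 0.275) + 0.842 × √(0.80 × 0.20 + 0.65 × 0.35)]² / 0.15² = 137.9, so 138 per group. The protocol states 137.

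For 15% dropout, 274 / 0.85 gives 323 and 274 × 1.15 gives 316. The stated 320 lies between them. No stated figure is wrong.

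**2. Log-rank power at the same rates.** The protocol gives none, so it is derived.
- Evaluable children: 320 × 0.85 = 272, or 136 per arm.
- Recoveries: 136 × (0.80 + 0.65) = 197.
- Recovery-rate ratio, with exponential times: ln(0.20) / ln(0.35) = 1.53.
- Schoenfeld: √(197.2 / 4) × ln(1.53) − 1.96 = 1.04, giving power of about 85%.

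**3. Effect of stratifying.** The size of any age effect is not in the protocol, so a range was simulated: 10,000 runs per cell, 272 children, control recovery 65% overall, treatment rate ratio 1.53 in both age groups, exponential times on a daily grid, and a 14-day window (7 days on each diet). Results are in per cent. The percentage split gives the slower-recovering age group first.

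| Rate ratio between age groups | Allocation | Power, plain | Power, stratified | Type I error, plain |
|---|---|---|---|---|
| 1.0 | 50:50, balanced within strata | 85.1 | 85.1 | 5.2 |
| 1.0 | 70:30, balanced within strata | 84.6 | 84.3 | 5.0 |
| 1.0 | 70:30, simple randomisation | 84.6 | 84.5 | 5.3 |
| 1.5 | 50:50, balanced within strata | 83.9 | 85.1 | 4.8 |
| 1.5 | 70:30, balanced within strata | 84.0 | 85.0 | 4.5 |
| 1.5 | 70:30, simple randomisation | 83.7 | 84.5 | 4.9 |
| 2.0 | 50:50, balanced within strata | 80.4 | 83.8 | 3.9 |
| 2.0 | 70:30, balanced within strata | 81.8 | 84.5 | 4.3 |
| 2.0 | 70:30, simple randomisation | 80.1 | 84.1 | 5.1 |
| 3.0 | 50:50, balanced within strata | 74.5 | 84.6 | 3.0 |
| 3.0 | 70:30, balanced within strata | 75.5 | 83.9 | 3.4 |
| 3.0 | 70:30, simple randomisation | 73.5 | 84.0 | 5.2 |

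The Monte Carlo standard error is √(0.85 × 0.15 / 10,000) = 0.4 points for power and √(0.05 × 0.95 / 10,000) = 0.2 points for type I error.

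The table should be read across each row. Because the ratio of 1.53 is held within each age group, overall intervention success drops a little below 80% as the age effect grows, so part of the fall down the plain column is not a cost of pooling.

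**4. What these ratios mean.** With equal age groups and 65% of controls recovering, the unrecovered share y in the slower group solves (y + yʳ) / 2 = 0.35 for rate ratio r.
- r = 1.5: y = 0.424, so recovery is 57.6% against 72.4%.
- r = 2: y = 0.475, so 52.5% against 77.5%.
- r = 3: y = 0.541, so 45.9% against 84.1%.

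A two-fold ratio is thus a gap of about 25 percentage points between age groups, and a three-fold ratio about 38.

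**The case against.** **The label may mean something else.** A life table does allow for unequal follow-up and withdrawal, and the Study withdrawal section makes that relevant. The sentence also answers a comment that is not reproduced, so this may be the intended sense. It follows that saying the test adjusts for nothing at all would be too strong. The objection does not rescue the word: allowing for censoring is not adjustment for a baseline factor, and readers will take it as such.

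**Detail belongs in an analysis plan.** This stands for the success comparison. No test is named there, a stratified one is not excluded, and leaving it open is no defect. It does not stand for the log-rank test, which the protocol both specifies and labels.

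**Any loss is conditional.** This stands. No statement in the protocol says that age predicts recovery, and choosing age as a stratification factor does not show it. A reader might infer that precision is certainly being thrown away. With no age effect the gain is nil, and at a ratio of 1.5 it is about one point.

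**The randomisation lists.** A reader might infer from the mention of a random table that the lists are unblocked, so that stratifying achieves nothing at the design stage. The protocol does not say whether blocks are used, and a random table can also generate blocked lists. No conclusion about imbalance is drawn here. The simulations cover both cases.

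**Conclusion.** The label is wrong in ordinary usage, and the age groups that govern randomisation are absent from the only time-to-event test specified. This can be read directly from the protocol and needs no assumption.

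The effect on power is modest and conditional: about 0 to 1 point if age is weakly prognostic, 3 to 4 points at a two-fold difference in recovery rates, and 8 to 10 points at a three-fold difference, which is a very large age effect. These sizes rest on exponential recovery times, a common treatment ratio in both age groups and 272 evaluable children. They apply to the log-rank test; the gain for the success-rate comparison was not simulated.

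Two stronger inferences are not supported. First, the plain test does not endanger the false-positive rate. Its type I error was at or near 5% with simple randomisation and below 5% when arms were balanced within prognostic age groups (3.9 to 4.3% at a ratio of 2, 3.0 to 3.4% at 3). Second, the sample size is not called into question: 137 per group and 320 in total both reproduce approximately, and log-rank power at the planning rates is about 85% when age has no effect.

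**What to change.** In the Statistical analysis section:

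1. Specify the time-to-cessation comparison as a log-rank test stratified by age group at entry (5-18 and 19-36 months).
2. Compare overall success with a Mantel-Haenszel relative risk and 95% confidence interval, stratified by the same two groups.
3. Use the word adjusted only for these stratified analyses. If the plain log-rank test is kept, call it an unadjusted time-to-cessation analysis.

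The cost is a change of wording before the data are analysed. No extra data are needed, because age at entry already decides which randomisation list is used. No extra children are needed, and where age has no effect the simulated power of the log-rank test is essentially unchanged (84 to 85% either way).

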Personnel: Investigators' salary support has been calculated by per cent of effort. Study Physician will help in taking medical history and physical examination in the hospital and also during home visits. Research Officer will organise the facilities in the hospital, arrange equipment and material needed for examination and training. S/he will also do data entry and will help in data analysis. Research assistant will be engaged in patients' recruitment, educate mothers/caregivers about preparation of feeding of diet, and also supervise the caregivers at home.

Equipment: Weighing scale and other measuring equipments will be purchased for anthropometric measurements. Computer accessories will also be needed.

Laboratory services: Cost of laboratory services has been calculated from the existing rates of laboratory services.

Principal Investigator: Last, first, middle _____

Other Support

Describe sources, amount, duration, and grant number of all other research funding currently granted to PI or under consideration. (DO NOT EXCEED ONE PAGE FOR EACH INVESTIGATOR)

1. WHO 47,000.00 for 1 year
2. Novartis Nutrition 89,000.00 for 2 years

Principal Investigator: Last, first, middle _____

Check List

After completing the protocol, please check that the following selected items have been included.

1. Face Sheet Included

2. Approval of the Division Director on Face Sheet

3. Certification and Signature of PI on Face Sheet, #9 and #10

4. Table on Contents

5. Project Summary

6. Literature Cited

7. Biography of Investigators

8. Ethical Assurance

9. Consent Forms

10. Detailed Budget

Answer to Reviewer # I

1. "Demonstrated ability of caregiver" has been omitted from the protocol. All patients fulfilling other entry criteria will be included. Caregivers of the patient who also do not have economic means for providing the advised diets, the ingredients of the study diet will be supplied during the study period.
2. The envelopes will be opened only after a patient has been irrevocably assigned to the study.
3. The mothers will be taught to prepare Diet B on day 6 when there will be no improvement of diarrhoea with Diet A for 5 days.
4. The patients will be followed up for 4 weeks after diarrhoea resolved.
5. Adjusted analysis will be done by construction of life tables of the patients of the study groups and will be compared by log rank test:
6. Addition of 1 g of salt to Diet A has been omitted.

